1.10.5 Exploratory efficacy variables

Exploratory efficacy variables will be analyzed separately for each independent cohort (TRAPS, HIDS, crFMF).

Inflammatory parameters (CRP, SAA)

CRP and SAA will be summarized descriptively by analysis visit for each cohort, by epoch and treatment groups (as defined in [section 1.3](#)).

In addition, the number and percentage of patients with CRP ≤ 10 mg/L, SAA ≤ 10 mg/L will also be presented.

Number and percentage of patients with CRP ≤ 10 mg/L, CRP $> 10 - < 15$ mg/L, CRP $\geq 15 - < 30$ mg/L, CRP ≥ 30 mg/L at day 15 will be presented by status of resolution of index flare and initial randomized treatment.

Number and percentage of patients with CRP ≤ 10 mg/L, CRP $> 10 - < 15$ mg/L, CRP $\geq 15 - < 30$ mg/L, CRP ≥ 30 mg/L at day 29 will be presented for patients initially receiving ACZ and having up-titration before day 29 by disease cohorts.

In addition, number and percentage of patients with the following categories will be summarized for CRP assessment before day 15, at day 15 and day 29 by initial randomized treatment by disease cohorts.

- CRP ≤ 10 mg/L
- CRP reduction less than 40% from baseline
- CRP reduction of $\geq 70\%$ from baseline
- CRP reduction of $\geq 40\%$ from baseline

In the final analysis, summary tables of CRP and SAA after patients taking ACZ885 will be shown by visit, from Baseline to last visit in Epoch 4.

PGA and PPGA Disease Activity, Key disease specific signs and symptoms

The efficacy outcomes measured on Likert scale, such as physician's global assessment of disease activity, physician's severity assessment of disease signs and symptoms, will be presented in frequency tables by analysis visit for each cohort, epoch and treatment groups (as defined in [section 1.3](#)).

Between-treatment differences for the proportion of patients with no disease activity based on PGA (PGA<1), no disease activity (rate overall severity<1) based on PPGA at Week 16 will be analyzed using a Fisher's exact test for each cohort, by randomized treatment group.

Patients needing dose escalation in the canakinumab arms, or who escape from placebo arms to canakinumab in the randomized treatment epoch (Epoch 2) or discontinued from the study due to any reason prior evaluating the endpoint at week 16, will be considered as having PGA ≥ 1 and PPGA ≥ 1 . Patient/parent's global assessment of disease activity (PPGA) will also be summarized for weekly averages using summary statistics. Week 0 will be average of PPGA score from day -7 to day 1, week 1 will be average of score from day 2 to day 7, week 2 will be average of score from day 8 to day 14 and so on.

In addition, Spaghetti plot will be provided by subject and cohort and initial randomized treatment for PGA assessment and Physician's severity assessment of disease signs and symptoms

In the final analysis, shifts in PGA score from baseline to end of Epoch 4 by treatment group for each cohort will be shown in figures. , Summary tables of PGA after patients taking ACZ885 will be shown by visit, from Baseline to last visit in Epoch 4.

Episodes of Fever

Number and duration of fever episodes collected in patient's diaries will be summarized within each cohort, epoch and treatment group (as defined in [section 1.3](#)). Plots of fever episodes per patient over time (displaying frequency and duration) and treatment group will also be presented. Treatment difference for time to first resolution of fever will be analyzed using a Cox proportional hazard regression model. The Kaplan-Meier estimates of the proportion of patients with first resolution of fever along with the associated 95% confidence intervals using the Greenwood's formula will be provided.

Rescue medication

Corticosteroids levels will be summarized descriptively by analysis visit for each cohort and by treatment group (as defined in [section 1.3](#)). In addition, the number and percentage of patients who reduce their corticosteroids maintenance dose at Week 16 compared to baseline, patients who take corticosteroids rescue medication and patients who take only NSAIDs rescue medication during the study, patients who take steroid level >0.2 mg/kg/day will also be presented. Between-treatment differences for the proportion of patients who are able to reduce their corticosteroids at Week 16 will be analyzed using a Fisher's exact test for each cohort. The analysis will only include subjects who were receiving corticosteroids at baseline.

Rescue medications are not collected visit wise in the study and are collected in summary page as part of concomitant medications. Rescue medications will be mapped to visits. Rescue medications shall be assigned to visit based on start and end date of the medication and corresponding visit date. For example, if visit date for visit 103 lies between start and end date of "VALISONE-G" corticosteroid then dose level of this concomitant medication will be assigned to visit 103. If there are more than one dose that are assigned to same visit then these

doses shall be added after converting the units to mg/kg/day. If there are no records of rescue medication for any visit then it shall be considered as 0 mg/kg/day dose.

Blinded escape

The number and percentage of patients who require blinded escape from Days 8 to 28 will be summarized by cohort and randomized treatment group.

Auto-Inflammatory Disease Activity Index (AIDAI)

Symptoms evaluated in the AIDAI diary will be summarized with each cohort and epoch (2 and 3) and by treatment group (as defined in [section 1.3](#)) for monthly score as sum of scores over a month. Spaghetti plot will be provided by subject and cohort and initial randomized treatment.

Time to first new flare in the randomized withdrawal epoch (Epoch 3)

Time to first new flare in Epoch 3 will be analyzed for patients re-randomized at the start of epoch 3. The two treatment groups (150mg q8w and placebo) will be compared using a one-sided log-rank test at the 2.5% significance level. The hazard ratio and its associated 95% two-sided confidence intervals will be estimated. Kaplan-Meier estimates of the probability to experience a flare event will be calculated from the start of the randomized withdrawal epoch. 95% confidence intervals using Greenwood's formula will be provided.

Patients who discontinued the study in epoch 3, or having an up-titration or escape from placebo group to canakinumab arm will be counted as having a flare in epoch 3. In this case the date of the premature subject withdrawal (PSW) visit, or resp. time of up-titration or escape is considered as the end date for the calculation of time to flare.

SF-12 Health Survey (SF-12)

SF-12 scores will be summarized (descriptively) by epoch (2 and 3), analysis visit, initial randomized treatment and treatment sequence (as defined in [section 1.3](#)) within each cohort. Only patients ≥ 18 years of age at baseline will be part of the analyses.

SF-12 measurements consists of 12 questions over eight subscales (physical function, pain, general and mental health, vitality, social function, physical and emotional health). The subscales can be aggregated to derive a physical-component summary score (PCS) and a mental-component summary score (MCS).

The score will be summarized for each subscale and for PCS and MCS.

Child Health Questionnaire – Parent Form 50 (CHQ-PF50)

Descriptive statistics will be used to summarize patient responses on the CHQ-PF50[®] Questionnaire by epoch (2 and 3), analysis visit, initial randomized treatment and treatment sequence (as defined in [section 1.3](#)), total score (Physical (PhS) and Psychosocial

(PsS) scores) and by domain within each cohort. Only patients $>5 <18$ years of age at baseline are included.

Sheehan Disability Scale (SDS v3)

SDS score by domain and global functional impairment score will be summarized by epoch (2 and 3), analysis visit, initial randomized treatment and treatment sequence (as defined in [section 1.3](#)) within each cohort.

Number of flares

The number of new flares by patient will be summarized by epoch and treatment arms within each cohort.

Disease-associated genetic mutations

Relationships between disease-associated genetic mutations and CRP/SAA/PGA values at Day 15 on patients randomized to Canakinumab will be analyzed by cohort. T-test will be used for mean comparison between genetic mutations for CRP and SAA, and wilcoxon rank sum test will be used for mean comparison between genetic mutations for PGA. Mean CRP, SAA, PGA at Day 15 were compared between

For cr-FMF cohort

- (i) all M694V gene vs overall cr-FMF canakinumab treated patients
- (ii) all M694V gene vs non-M694V gene
- (iii) M694V heterozygous vs homozygous

For HIDS cohort

- (i) all V377I gene vs overall HIDS canakinumab treated patients
- (ii) all V377I gene vs non-V377I gene
- (iii) V377I heterozygous vs homozygous

For TRAPS cohort

- (i) all R92Q gene vs overall TRAPS canakinumab treated patients
- (ii) all R92Q gene vs non-R92Q gene
- (iii) R92Q heterozygous vs homozygous

In the T-test procedure, Pooled and Satterthwaite methods for the p-value were used depending on the test on equality of variances.

In the Npar1way procedure, p-value from Exact test was taken given the relatively small sample size of patients.

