Exclusion criteria	
 Use of the following therapies (within varying protocol defined timeframes): Corticosteroids (oral prednisone) >0.2 mg/kg/day (or greater than the maximum of 15 mg/day for children over 60 kg), anakinra, canakinumab, rilonacept, tocilizumab, TNF inhibitors, abatacept, tofacitinib, rituximab, leflunomide, thalidomide, cyclosporine, intravenous immunoglobulin, 6-Merceptopurine, azathioprine, cyclophosphamide, or chlorambucil, intra-articular, peri-articular or intramuscular corticosteroid injections, any other investigational biologics History of malignancy of any organ system (other than localized basal cell carcinoma of the skin or in-situ cervical cancer), treated or untreated Significant medical diseases, including but not limited to the following: 
 History of organ transplantation Elevated alanine aminotransferase (ALT) ≥ 3x ULN Elevated aspartate aminotransferase (AST) ≥ 3x ULN Increase in total bilirubin defined as per Common Terminology Criteria (CTC) Grade ≥ 2 Serious hepatic disorder (Child-Pugh scores B or C) Chronic Kidney Disease as per NKF stages ≥ 4 Thyroid disease Diagnosis of active peptic ulcer disease Coagulopathy Significant CNS effects including vertigo and dizziness Any conditions or significant medical problems which immunocompromise the patient and/ or places the patient at unacceptable risk for immunomodulatory therapy, e.g. 
 Absolute neutrophil count decreased as per CTC Grade ≥ 1 Thrombocytopenia CTC Grade ≥ 1 Any active or recurrent bacterial, fungal (with exception of onychomycosis) or viral infection

	
 d. HIV infection, Hepatitis B or Hepatitis C infections e. Presence of tuberculosis f. Requirement for administration of antibiotics against latent TB g. Clinical evidence or history of multiple sclerosis or other demyelinating diseases, or Felty's syndrome • Live vaccinations within 3 months prior to the start of the trial, during the trial, and up to 3 months following the last dose
Investigational and reference therapy	
 • Canakinumab • Placebo
Efficacy assessments	
 • PGA • Physician's severity assessment of key disease-specific signs and symptoms • Rescue medication use • Review eDiary instructions • Patient/Parent Global Disease Activity (PPGA) • Auto-Inflammatory Disease Activity Index (AIDAI)

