4.2 Exclusion criteria

Patients fulfilling any of the following criteria are not eligible for inclusion in this study. No additional exclusions may be applied by the investigator, in order to ensure that the study population will be representative of all eligible patients.

1. Use of the following therapies:
 - a. Corticosteroids (prednisone equivalent > 0.2 mg/kg/day [or greater than the maximum of 15 mg/ day for children over 60 kg]) within 1 week prior to Baseline
 - b. Anakinra within 24 hours prior to Baseline
 - c. Canakinumab within 3 months prior to Baseline (*not applicable for patients rolling-over from CACZ885D2203/ CACZ885D2207M*)
 - d. Rilonacept within 4 weeks prior to Baseline
 - e. Tocilizumab within 6 weeks prior to Baseline
 - f. Etanercept within 2 weeks prior to Baseline
 - g. Infliximab within 4 weeks prior to Baseline
 - h. Adalimumab within 6 weeks prior to Baseline
 - i. Golimumab within 6 weeks prior to Baseline
 - j. Certolizumab within 6 weeks prior to Baseline
 - k. Abatacept within 7 weeks prior to Baseline
 - l. Tofacitinib within 24 hours prior to Baseline
 - m. Rituximab within 24 weeks prior to the Baseline
 - n. Leflunomide within 8 weeks prior to the Baseline
Documentation of a completion of a full cholestyramine elimination treatment after most recent leflunomide use will be required.
 - o. Thalidomide within 4 weeks prior to Baseline
 - p. Cyclosporine within 4 weeks prior to Baseline
 - q. Intravenous immunoglobulin (i.v. Ig) within 8 weeks prior to Baseline
 - r. 6-Mercaptopurine, azathioprine, cyclophosphamide, or chlorambucil within 12 weeks prior to Baseline
 - s. Intra-articular, peri-articular or intramuscular corticosteroid injections within 4 weeks prior to Baseline
 - t. Any other investigational biologics within 3 half-lives prior to the Baseline visit
 - u. Any other investigational drugs, other than investigational biologic treatment, within 30 days (or 3 months for monoclonal antibodies) or 3 half-lives prior to the Baseline visit, whichever is longer
2. History of hypersensitivity to any of the study drugs or to drugs of similar chemical classes or to any of the excipients.
3. History or current diagnosis of ECG abnormalities indicating significant risk of safety for patients participating in the study such as:

- a. Concomitant clinically significant cardiac arrhythmias, e.g., sustained ventricular tachycardia, and clinically significant second or third degree AV block without a pacemaker

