5.5.6 Rescue medication

Increase of corticosteroid maintenance dose or intermittent steroid treatment up to the dose detailed in [Table 5-1](#) may be used as rescue therapy.

Standard doses of NSAIDs can be used from Day 15 inclusive on an as needed basis to treat the sign and symptoms of TRAPS, HIDS or crFMF during acute flares at the discretion of the investigator. Before Day 15, NSAIDs should not be used for treating any signs or symptoms of the index flare.

Use of rescue medication must be recorded on the concomitant medications page in the CRF.

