5.5.8 Prohibited Treatment

Use of the treatments displayed in [Table 5-1](#) is NOT allowed after Screening.

Table 5-1 Prohibited treatment

Medication	Action to be taken
Corticosteroid maintenance (prednisone equivalent > 0.2 mg/ kg/ day or greater than the maximum of 15 mg/ day for children over 60 kg).	Investigational treatment does not need to be discontinued as a result of this protocol deviation (PD)
Anakinra	Investigational treatment to be discontinued ²
Rilonacept, tocilizumab, rituximab and any other biologics ¹ (investigational or marketed)	Investigational treatment to be discontinued ²
Etanercept, adalimumab, infliximab, or any TNF inhibitor (investigational or marketed)	Investigational treatment to be discontinued ²
Leflunomide, thalidomide, cyclosporine, or i.v. Ig	Investigational treatment to be discontinued ²
Tofacitinib	Investigational treatment to be discontinued ²
6-Mercaptopurine, azathioprine, cyclophosphamide, or chlorambucil	Investigational treatment to be discontinued ²
Intra-articular, peri-articular or intramuscular corticosteroid injections	Investigational treatment to be discontinued ²
Any other investigational non-biological drug	Investigational treatment to be discontinued ²
Any live vaccination ¹	Investigational treatment to be discontinued ²
Treatment for tuberculosis	Investigational treatment to be discontinued

¹ It is recommended not to initiate any live vaccination or biologic treatment until 3 months after the last dose of investigational treatment. Killed or inactivated vaccines may be permitted according to the investigator's discretion.

² Investigational treatments must be permanently discontinued but patient will remain in the study and will be followed-up for safety.

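### SAP 1.10.5 sums corticosteroid doses and applies the 0.2 mg/kg/day cut with no prednisone-equivalent conversion, so patients on steroids of other potency can be misclassified in exploratory outputs

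*SAP*

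**What the plan says.** The Rescue medication part of SAP 1.10.5 assigns each medication record to a visit when the visit date lies between the record's start and end dates. In its worked example for a named corticosteroid product, the "dose level of this concomitant medication will be assigned to visit 103". Where several records fall on one visit, "doses shall be added after converting the units to mg/kg/day". A visit with no record gets a dose of zero.

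The same part summarises corticosteroid levels by visit and states that "patients who take steroid level >0.2 mg/kg/day will also be presented". It also compares the arms, by Fisher's exact test within each cohort, on the share of patients who reduce corticosteroids by Week 16. That comparison is restricted to patients on corticosteroids at baseline.

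The figure of 0.2 mg/kg/day comes from the protocol:

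- Exclusion criterion 1a (Section 4.2): "prednisone equivalent > 0.2 mg/kg/day".
- Table 5-1 (Section 5.5.8): "Corticosteroid maintenance (prednisone equivalent > 0.2 mg/ kg/ day or greater than the maximum of 15 mg/ day for children over 60 kg".
- Protocol summary, exclusion criteria: "Corticosteroids (oral prednisone) >0.2 mg/kg/day".
- Section 5.5.6 ties rescue use to the Table 5-1 dose: "Increase of corticosteroid maintenance dose or intermittent steroid treatment up to the dose detailed in" that table.

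Neither the SAP nor protocol Section 9 mentions prednisone equivalents in the analysis or gives a conversion table.

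**The concern.** A change of units to mg/kg/day puts doses on a common weight basis but not on a common potency basis. The protocol's wording shows that more than one corticosteroid was expected and that milligrams of different steroids were not to be compared directly. The SAP keeps the number 0.2 and drops the scale that gives it meaning.

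Three outputs could be affected: the steroid level by visit, the count above 0.2 mg/kg/day and, depending on how it is programmed, the Week 16 steroid-reduction comparison. A patient on a more potent steroid could exceed 0.2 in prednisone equivalents and not be counted; a patient on a less potent one could be counted without exceeding it. A change of drug could look like a change of dose.

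**Working it through.** The plan states no figure on this point, so there is nothing to reproduce. The check compares two definitions.

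**Inputs.** From SAP 1.10.5: doses in mg/kg/day are added, and the cut is above 0.2. From protocol Section 4.2 and Table 5-1: the limit is above 0.2 mg/kg/day in prednisone equivalents. Assumed, because the documents give no potencies: a factor f, the mg of prednisone equivalent per mg of the steroid taken, from 0.25 to 7, with f = 1 for prednisone.

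**Formulas.** For doses d_i in mg/kg/day at a visit:

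- SAP total: S = sum of d_i, counted if S > 0.2.
- Protocol scale: E = sum of f_i × d_i, above the limit if E > 0.2.

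S and E are equal for every set of doses only if every f_i = 1.

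**One steroid.** The own-drug dose that equals the protocol limit is 0.2/f. A raw dose of 0.2 equals 0.2 × f in prednisone equivalents.

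| f (assumed) | Own-drug dose at the limit, 0.2/f | Raw 0.2 expressed as prednisone equivalent, 0.2 × f |
|---|---|---|
| 0.25 | 0.80 | 0.05 |
| 0.8 | 0.25 | 0.16 |
| 1 | 0.20 | 0.20 |
| 1.25 | 0.16 | 0.25 |
| 5 | 0.04 | 1.0 |
| 7 | 0.029 | 1.4 |

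For f above 1, doses above 0.2/f and up to 0.2 are missed. For f below 1, doses above 0.2 and up to 0.2/f are counted in error. So the problem does not need a sum; a single steroid other than prednisone is enough.

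**Two steroids.**

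- Missed: 0.10 prednisone plus 0.05 of a steroid with f = 5. S = 0.15, not counted. E = 0.10 + 5 × 0.05 = 0.35, above the limit. For this mix the two rules disagree once f exceeds (0.2 − 0.10)/0.05 = 2.
- Counted in error: 0.15 prednisone plus 0.08 of a steroid with f = 0.25. S = 0.23, counted. E = 0.15 + 0.25 × 0.08 = 0.17, below the limit. Here they disagree when f is at or below (0.2 − 0.15)/0.08 = 0.625.

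**Week 16 reduction, if the visit-level dose is its input.** The raw rule compares d at Week 16 with d at baseline; the equivalent rule compares f × d at each time.

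- Same steroid throughout: f multiplies both sides and cancels.
- Steroids stopped: the Week 16 dose is 0 on either scale.
- Switch, for example 0.15 prednisone to 0.05 of a steroid with f = 5: raw falls from 0.15 to 0.05, a reduction; the equivalent rises from 0.15 to 5 × 0.05 = 0.25, an increase.

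Only a switch or a changing mix can produce a disagreement.

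**The second limb of Table 5-1.** The SAP count also omits the 15 mg/day limb for children over 60 kg. The two limbs meet at 15/0.2 = 75 kg. Above that weight a child can exceed 15 mg/day without exceeding 0.2 mg/kg/day; at 80 kg, 15 mg/day is 15/80 = 0.1875 mg/kg/day.

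**The case against.** The SAP does not forbid an equivalence step. It speaks of converting units and is silent on potency, so this could be called missing detail that programming specifications would supply. Part of that stands: nobody can tell from the text what was programmed. But the sentence is an operative rule with a stated target unit, and followed literally it gives the wrong scale for any steroid not equipotent with prednisone. That is more than an omission.

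A reader might infer three stronger things that the documents do not support.

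- **That the count above 0.2 is wrong.** It errs only for patients whose steroid differs in potency from prednisone, and only when the difference moves them across 0.2. The documents give no steroid mix, and for a patient on prednisone alone the 0.2 mg/kg/day cut is exact.
- **That the Week 16 Fisher test is built on the summed dose.** The mapping and adding rule is written for rescue medication, while the reduction concerns the maintenance dose. Using the same visit-level dose is a plausible reading, since no other rule for one is given, but it is not stated.
- **That compliance with the protocol limit would be misreported.** The SAP does not present this count as a compliance check. Table 5-1 classes excess maintenance steroid as a protocol deviation, and SAP 1.6 tabulates deviations separately.

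The potency range is also an assumption. It shows the direction and mechanism of the error, not its effect on any result.

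**Conclusion.** Wrong as written, but minor and exploratory. The rule in SAP 1.10.5 and its 0.2 mg/kg/day cut are not on the prednisone-equivalent scale on which the protocol defines that limit, and nothing else in the SAP restores it. The by-visit steroid level and the count above 0.2 can therefore misclassify patients taking a steroid of different potency, in either direction. The Week 16 reduction comparison is exposed only if it uses the same visit-level dose, and then only for patients who switch or mix steroids.

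How many patients this touches cannot be derived from the documents. The conversion of a raw 0.2 to between 0.05 and 1.4 mg/kg/day rests wholly on the assumed factors of 0.25 to 7. The primary responder definition, the H1 to H5 testing sequence and the sample size do not use these doses.

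**What to change.** In SAP 1.10.5:

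1. Convert each systemic corticosteroid dose to prednisone-equivalent mg/kg/day with a table fixed in the SAP, before doses at a visit are added.
2. Apply the 0.2 cut to the converted total, and align its wording with Table 5-1, including the 15 mg/day limb. The protocol summary's reference to oral prednisone should be reconciled with the prednisone-equivalent wording in Section 4.2 and Table 5-1.
3. State that records without a meaningful systemic mg/kg/day dose are listed and not summed. The present rule has no restriction by route, and Table 5-1 itself puts intra-articular, peri-articular and intramuscular corticosteroid injections on a separate row from maintenance steroid.
4. State which dose variable the Week 16 reduction comparison uses; if it is the visit-level dose, use the converted one.

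The cost is a lookup table and a few lines in the SAP and its programming. No new data item is needed if drug, dose, route and dates are recorded on the concomitant medication page. The change applies the protocol's own scale and alters no clinical rule.

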	Day 113	Day 141	Day 169	Day 197	Day 225	Day 253	Cumulative dose in mg
Dose: 150mg q8 with no flare	X 150mg		X 150mg		X 150mg		450mg
1 flare between D225- D253	X 150mg		X 150mg		X 150mg	X 150mg	600mg
1 flare between D197- D225	X 150mg		X 150mg		X 150mg	X 150mg	600mg
1 flare between D169- D197	X 150mg		X 150mg	X 150mg	X 150mg	X 150mg	750mg
1 flare between D141- D169	X 150mg		X 150mg	X 150mg	X 150mg	X 150mg	750mg
1 flare between D113- D141	X 150mg	X 150mg	X 150mg	X 150mg	X 150mg	X 150mg	900mg

Therefore for a patient taking initially 150mg q8w at the start of epoch 3 and having one flare in epoch 3, the range of cumulative dose over 24 weeks will be [600 mg-900 mg].

Notes: 1. Earlier the flare occurs, higher the cumulative dose is
2. More flares => increase of cumulative dose, but stable after 5 flares

Cumulative dose calculation for epoch 3:

For Patients weighing ≥ 7.5 kg and ≤ 40 kg, the dose is derived in mg/kg ie. Actual total dose (ml) $\times 150$ mg / Weight(kg) at visit.

- If the sum of the dose (mg/kg) in Epoch 3 is ≤ 7 mg/kg then the patient will be assigned to the dose level category <600 mg.
- If the sum of the dose (mg/kg) in Epoch 3 is >7 mg/kg - ≤ 15 mg/kg then the patient will be assigned to the dose level category ≥ 600 mg- <1200 mg.
- If the sum of the dose (mg/kg) in Epoch 3 is >15 mg/kg then the patient will be assigned to the dose level category ≥ 1200 mg.

For Patients weighing <7.5 kg, the dose is derived in mg/kg ie. Actual total dose (ml) $\times 75$ mg / Weight(kg) at visit.

[figure not shown]
- If the sum of the dose (mg/kg) in Epoch 3 is ≤ 7 mg/kg then the patient will be assigned to the dose level category <600 mg.
- If the sum of the dose (mg/kg) in Epoch 3 is >7 mg/kg - ≤ 15 mg/kg then the patient will be assigned to the dose level category ≥ 600 mg- <1200 mg.
- If the sum of the dose (mg/kg) in Epoch 3 is >15 mg/kg then the patient will be assigned to the dose level category ≥ 1200 mg.

Open-label treatment epoch (Epoch 4):

As few patients are expected having no flare in epoch 4 for 72 weeks, then safety and efficacy data will be displayed using the cumulative dose over the 72 weeks in Epoch 4 in the following way:

----- Cumulative dose in mg over 72 weeks -----
<2700mg $\geq 2700\text{mg} - < 5400\text{mg}$ $\geq 5400\text{ mg}$

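### The Week 16 test of reduced corticosteroid maintenance dose uses a level that adds up every steroid record at the visit, so the end of a short course spanning baseline counts as a maintenance reduction.

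*SAP*

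**What the plan says.** In SAP 1.10.5 (Exploratory efficacy variables, under Rescue medication) the endpoint is "the number and percentage of patients who reduce their corticosteroids maintenance dose at Week 16 compared to baseline". The arms are to be compared by Fisher's exact test, within each cohort, on the "proportion of patients who are able to reduce their corticosteroids at Week 16". The denominator is set by one sentence: "The analysis will only include subjects who were receiving corticosteroids at baseline".

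The same section gives the only derivation of a steroid level:

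- Source: "Rescue medications are not collected visit wise in the study and are collected in summary page as part of concomitant medications".
- Mapping: "Rescue medications shall be assigned to visit based on start and end date of the medication and corresponding visit date".
- Several records at one visit: "doses shall be added after converting the units to mg/kg/day".
- No record at a visit: the level is zero on the same mg/kg/day scale.

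The section does not say which weight converts mg to mg/kg, and it has no rule for telling maintenance records from intermittent ones.

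Protocol 5.5.6 does keep the two apart. It allows as rescue "Increase of corticosteroid maintenance dose or intermittent steroid treatment up to the dose detailed in" Table 5-1. Protocol 4.2 (criterion 1a) excludes corticosteroids in the week before Baseline only above 0.2 mg/kg/day prednisone equivalent (with a 15 mg/day maximum for children over 60 kg). Protocol 4.1.2 to 4.1.4 require an active flare at randomization.

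**The concern.** The endpoint is named for the maintenance dose, but the derived level is total corticosteroid on the visit date. The two differ whenever a temporary course is running, and baseline is a likely time for one because every randomized patient is then in flare. A course that covers Day 1 raises the baseline level, and its planned end lowers the later level. The rule reads that fall as a reduced maintenance dose.

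The denominator adds to this. A patient who has never taken maintenance steroid enters the analysis because of a short course at baseline, and can then be counted as a success.

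The unstated weight is a second, separate gap. If each visit's own weight is used, a growing child on an unchanged mg dose has a falling mg/kg/day level.

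At stake is the meaning of a planned between-arm test: it could partly reflect temporary courses and weight change instead of steroid sparing.

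**Working it through.** The documents give no number of steroid users, expected reduction rate or power for this endpoint, so there is no planned figure to reproduce. The check applies the SAP rule to simple cases. All doses and weights below are assumed for illustration.

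**Rule.** Level at a visit = (sum of mg/day over records whose dates span the visit) / weight in kg, or 0 if there is no record. A patient is reduced if the Week 16 level is below the baseline level; SAP 1.10.5 sets no minimum change.

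**Short courses, 50 kg, weight constant.** The doses do not exceed the Protocol 4.2 limit, since 10/50 = 0.20 mg/kg/day.

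| Case | Baseline | Week 16 | Rule says | Maintenance records only |
|---|---|---|---|---|
| 10 mg/day course spanning Day 1, ended before Day 113, no maintenance | 10/50 = 0.20 | 0 | reduced | not in the denominator |
| Maintenance 5 mg/day unchanged, plus 5 mg/day course at baseline | (5+5)/50 = 0.20 | 5/50 = 0.10 (−50%) | reduced | 0.10 to 0.10, not reduced |
| Maintenance cut from 10 to 5 mg/day, plus 5 mg/day course at Week 16 | 10/50 = 0.20 | (5+5)/50 = 0.20 | not reduced | 0.20 to 0.10, reduced |

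The first two rows follow from the text as written and need no assumption about weight. The third shows the same rule hiding a real reduction.

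**Weight.** Protocol 6.5.3 records weight to 0.1 kg, and Protocol Table 6-1 schedules it at every Epoch 2 visit. If visit weight is used:

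- 5 mg/day unchanged, 25.0 to 25.1 kg: 5/25.0 = 0.2000, 5/25.1 = 0.1992 (−0.4%), reduced.
- 5 mg/day unchanged, 25.0 to 25.8 kg: 5/25.8 = 0.1938 (−3.1%), reduced.
- 10 mg/day unchanged, 70 to 72 kg: 10/70 = 0.1429, 10/72 = 0.1389 (−2.8%), reduced.
- Dose cut from 10 to 9.5 mg/day, 50 to 47 kg: 10/50 = 0.2000, 9.5/47 = 0.2021, not reduced, so a true cut is missed.
- Dose rescaled to stay at 0.2 mg/kg/day: no change, not reduced.

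If baseline weight is used at both visits, unchanged 5 mg/day gives 5/25.0 = 0.2000 both times, and the weight effect disappears.

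**What misclassification could cost.** Assume true reduction rates of 60% and 10%, and that a fraction m of true non-reducers in both arms is counted as reduced. The observed rates are 0.6 + 0.4m and 0.1 + 0.9m. The test is two-sided Fisher at 5%.

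| m | Observed rates | Difference | Power, 5 per arm | 10 per arm | 15 per arm |
|---|---|---|---|---|---|
| 0 | 60% v 10% | 50 points | 22% | 47% | 74% |
| 0.3 | 72% v 37% | 35 points | 11% | 18% | 32% |
| 0.6 | 84% v 64% | 20 points | 3% | 6% | 12.5% |

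This shows dilution when the error is equal in both arms. It is not an estimate for this trial.

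**The case against.** The best defence is that the SAP recognises the distinction. It lists reduction of maintenance dose separately from patients taking steroid rescue, and the adding rule applies only when several doses fall on one visit. Nor does it say outright that the reduction is judged on the mg/kg/day level. The separate label stands, but a label is not a derivation. The date mapping and the zero rule apply to single records too, no other steroid level is defined, and the denominator sentence admits any baseline user.

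A second defence is that low-dose flare courses on Day 1 may be rare. Use above the limit in the prior week is excluded, screening is meant to bring patients to a stable regimen (Protocol 3.1.1), and Protocol 3.6 describes corticosteroids as having limited efficacy except at very high doses. This is fair: the frequency is unknown. It does not show that courses are absent. Protocol 5.5.6 gives NSAIDs a Day 15 start but sets none for steroid.

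A third is that counting any decrease is a legitimate definition. That stands, and the absence of a threshold is not itself the fault.

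Two stronger readings are tempting. One is that any weight gain counts as a reduction. The documents do not support this. SAP 1.3 does divide by "Weight(kg) at visit", but that is for cumulative canakinumab dose in Epoch 3 in patients up to 40 kg. For steroids the weight is simply not specified. The other is that the error favours canakinumab. Nothing in the documents describes weight change by arm, the error can run either way, and placebo patients with unresolved or new flares can move to canakinumab from Day 8 (Protocol 3.1.2.2) or Day 29 (Protocol 3.1.2.3).

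**Conclusion.** The concern holds for the short-course mechanism: followed as written, SAP 1.10.5 counts the end of a course spanning baseline as a reduced maintenance dose. This requires only that the course cover the baseline visit date and that the total be lower at Week 16. The weight issue is an ambiguity that may create or hide a reduction, and it arises only if visit weight is used.

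In the illustrated cases the apparent reduction is 50% to 100% from a course ending, against 0.4% to 3.1% from weight gain. How often either occurs, and the net direction between arms, cannot be determined from the documents. The steroid endpoint is exploratory and lies outside H1 to H5, so the primary and secondary conclusions are untouched. The change is still worth making, because the endpoint has a planned test and its name promises something the derivation cannot identify.

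**What to change.** Amend SAP 1.10.5 for this endpoint as follows:

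- Compare maintenance dose in mg/day prednisone equivalent, or in mg/kg/day with baseline weight used at both visits.
- Define baseline maintenance from records already ongoing before the index-flare onset, which is recorded on the eCRF (Protocol 3.1.1).
- Leave intermittent and rescue courses out of the denominator and out of both the baseline and the Week 16 maintenance dose.
- Keep the all-records mg/kg/day level for the descriptive summaries and for the count above 0.2 mg/kg/day, and state which weight it uses.

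The medication dates and doses are already collected, so the cost is a few sentences and a small programming change. The denominator may shrink, because patients with only a short course at baseline drop out. The documents do not say whether the medication page records the reason for use. If it does not, records that dates alone cannot settle should be classified without knowledge of treatment arm.
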